#### 7.1.2 Treatment and Follow-up of AEs

All AEs, especially those that could be related to study medication, should be followed-up until they have returned to baseline status or stabilized. If after follow-up, return to baseline status or stabilization cannot be established an explanation should be recorded on the eCRF.

#### 7.1.3 Laboratory Test Abnormalities

Any treatment-emergent abnormal laboratory result that is clinically significant, should be recorded as a single diagnosis, if possible, on the AE page in the eCRF.

#### 7.1.4 Follow-up of Abnormal Laboratory Test Values

In the event of medically significant unexplained abnormal laboratory test values, the tests should be repeated and followed up until they have returned to the normal range or baseline and/or an adequate explanation of the abnormality is found. If a clear explanation is established it should be recorded on the AE page of the eCRF.

### 7.2 Handling of Safety Parameters

#### 7.2.1 Reporting of AEs

All new adverse events occurring during the study should be recorded on the AE page of the eCRF. Adverse events that occur intermittently should be recorded as one AE. Adverse events should be collected and reported from randomization to trial completion.

#### 7.2.2 Reporting of Serious Adverse Events

Any clinical AE or abnormal laboratory test value that is serious [as defined in section 7.1.1.3 above] and which occurs during the course of the study must be reported to the sponsor within 24 hours of the investigator becoming aware of the event.

Related Serious Adverse Events MUST be collected and reported regardless of the time elapsed from the last study medication administration, even if the study has been closed.

Like AEs in general, unrelated Serious Adverse Events must be collected and reported during the study and to trial completion.

The definition and reporting requirements of ICH Guideline for Clinical Safety Data Management, Definitions and Standards for Expedited Reporting, Topic E2 will be adhered to. Complete information can be found in Appendix 2.

#### 7.2.3 Pregnancy

A female subject must be instructed to stop taking the study medication and immediately inform the investigator if she becomes pregnant during the study. The investigator should report all pregnancies within 24 hours to the sponsor. The investigator should counsel the subject, discuss the risks of continuing with the pregnancy, and the possible effects on the fetus. Monitoring of the subject should continue until conclusion of the pregnancy.

Pregnancies occurring up to 90 days after the completion of the test medication must also be reported to the investigator.

### 7.3 Warnings and Precautions

No evidence available at the time of the approval of this study protocol indicated that special warnings or precautions were appropriate, other than those noted in the Investigators' Brochure.

## 8. STATISTICAL CONSIDERATIONS AND ANALYTICAL PLAN

### 8.1 Primary and Secondary Study Endpoints

#### 8.1.1 Primary Endpoint

The primary endpoint of this study is the time from randomization to first occurrence of any component of the composite endpoint as adjudicated by the CEC. Components of the primary endpoint are:

- Cardiovascular death
- Resuscitated cardiac arrest
- Non-fatal MI
- Non-fatal stroke

#### 8.1.2 Secondary and Exploratory Endpoints

The key secondary endpoints of this study are listed below.

##### Time to first occurrence of:

- The composite of CV death, resuscitated cardiac arrest, non-fatal MI, non-fatal stroke, or hospitalization for ACS (with ECG abnormalities) requiring coronary revascularization
- The composite of CV death, resuscitated cardiac arrest, non-fatal MI, non-fatal stroke, hospitalization for ACS (with ECG abnormalities), or unanticipated coronary revascularization
- The composite of all cause death, resuscitated cardiac arrest, non-fatal MI, or non-fatal stroke

Other secondary endpoints are listed below:

##### Time to first occurrence of

- The composite of CV death, resuscitated cardiac arrest, non-fatal MI, non-fatal stroke, or hospitalization for new or worsening heart failure
- The composite of CV death, resuscitated cardiac arrest, non-fatal MI, non-fatal stroke, hospitalization for ACS (with ECG abnormalities) requiring coronary revascularization, or hospitalization for new or worsening heart failure
- The composite of all-cause death, resuscitated cardiac arrest, non-fatal MI, non-fatal stroke, or hospitalization for new or worsening heart failure
- Fatal or non-fatal MI
- All-cause death

Exploratory endpoints are listed below

Healthcare resource utilization information

Change from baseline for:

- Blood levels of TC, TG, LDL-C, and HDL-C
- Blood levels of hsCRP

### 8.1.3 Safety

Safety of the treatment will be evaluated by AEs and vital signs.

## 8.2 Statistical and Analytical Methods

### 8.2.1 Sample Size

The sample size calculation is based on the primary endpoint. Under the following assumptions:

- an expected relative risk reduction of 22% and
- a statistical significance defined as a two-sided alpha of 0.05

the trial would have 85% power if it continues until at least 582 primary CEC adjudicated events occur in the combined treatment groups.

The total number of subjects to randomize, 6000, is chosen so that the expected number of events is at least approximately 582. It is based on the following assumptions, which were reviewed according to actual and planned recruitment rate:

- a 2.8-year recruitment period;
- a 1% yearly lost to follow-up rate; and
- a 7% event rate at 2 years following randomization in the placebo group.

Sample size was calculated using nQuery, version 7.0.

### 8.2.2 Analysis Populations

#### 8.2.2.1 Exclusion of Data from Analysis

Subjects will be completely excluded from analyses if they do not satisfy the criteria for inclusion in the specified analysis population, as defined below. If a subject satisfies the criteria for inclusion in an analysis population then no data from that subject will be excluded from use.

#### 8.2.2.2 Intent to Treat (ITT) Population

All subjects randomized will be included in the ITT population.

#### 8.2.2.3 Per-Protocol Population

A per-protocol population is defined as patients who meet all inclusion/exclusion criteria, are determined to be at least 80% compliant to study medication, and have completed the study with no premature study or medication discontinuation. This population will be used only in the context of exploratory analysis as described in section 8.2.4.3.

#### 8.2.2.4 Safety Analysis Population

All subjects who received at least one dose of treatment will be included in the safety analysis population. Subjects will be assigned according to the true treatment received for analysis purposes.

#### 8.2.2.5 Co-Diagnostic Analysis: Intent-to-Diagnose (ITD)

Patients who provide written informed consent and have blood drawn for screening will be tested for RS1967309 of ADCY9 by the cobas® ADCY9 Genotype CTA. Patients with AA genotype results will be allowed to proceed in the study and be further evaluated for eligibility into the study treatment phase and patients with non-AA genotype will be excluded from the study; however, demographic data for both the AA and non-AA groups will be recorded for evaluation of the cobas® ADCY9 Genotype CTA as a companion diagnostic for dalcetrapib. Patients who have a biologic sample obtained after Informed Consent are part of the Intent-to-Diagnose population.

### 8.2.3 Efficacy Analysis

#### 8.2.3.1 Primary Analysis

A stratified Cox proportional hazards model will be used to analyze the primary endpoint. Time to event will start at randomization and subjects who are lost to follow-up (while event free) will be censored at the time that they are last known to be event free. The strata will be defined by region (Eastern Europe, Western Europe, North America, South America, and other) and the ACS index event (MI or ACS [ECG abnormalities without biomarkers], see sections 4.1.1 and 4.1.2).

The null and alternative hypotheses to be tested with the above Cox model are:

$$H_0: \lambda = 1 \text{ vs. } H_A: \lambda \neq 1$$

Where  $\lambda$  is the, assumed constant, hazard ratio for the time to occurrence of the composite events of the primary endpoint for the dalcetrapib and placebo treated groups. The hazard ratio, within strata, will be assumed to depend on treatment alone. The estimated hazard ratio will be presented with a 95.2% confidence interval (CI) and a p-value.

The primary analysis will be based on the ITT population and conducted at the 0.048 significance level to account for interim assessments of efficacy as outlined in section 8.2.3.4.

### 8.2.3.2 Secondary and Exploratory Analysis

For the secondary endpoints that are expressed as time to event, an analysis similar to that for the primary endpoint will be conducted.

The changes from baseline in TC, TG, LDL-C, HDL-C and hsCRP levels will be compared between treatment groups using an analysis of covariance (ANCOVA) adjusting for baseline value and for the two stratification factors, ACS index event type and region. Specifically, the null and alternative hypotheses to be tested are:

$$H_0: \Delta_{\text{placebo}} = \Delta_{\text{dalcetrapib}} \text{ VS.}$$

$$H_A: \Delta_{\text{placebo}} \neq \Delta_{\text{dalcetrapib}}$$

where  $\Delta_{\text{placebo}}$  is the change in the placebo group and  $\Delta_{\text{dalcetrapib}}$  is the change in the dalcetrapib group. Estimates of treatment effect will be presented with 95% CI and p-values.

Secondary and exploratory analyses will be conducted on the ITT population. In order to control the Type I error that results from the multiplicity of endpoints, the key secondary endpoints will be formally tested using the Hochberg's step-up procedure only if the primary analysis results in significant treatment effect at  $p < 0.048$ . Otherwise, statistical tests for the secondary endpoints will be presented solely for illustrative purposes.

### 8.2.3.3 Sub-population Analyses

For illustrative purposes, the following factors:

- Geographic location
- Age
- Gender
- Race
- BMI
- Diabetes

may be used to define subgroups of subjects within which the primary and selected secondary efficacy endpoints will be evaluated using Cox proportional hazards models similar to the ones described in section 8.2.3.1, adding to the models a term for the factor defining the subgroup and a term for the interaction between the factor and the treatment group. This interaction term will be tested at the 0.1 significance level and will determine whether the treatment effect is affected by the presence of the factor. In addition, under the proposed models, the treatment effect will be estimated and presented with 95%

confidence intervals within subgroups. The sub-population analyses would be conducted on the ITT population.

#### 8.2.3.4 Interim Analysis

When approximately 70% (408) of the primary study endpoints have occurred and been positively adjudicated, an interim analysis will be conducted by the independent Data Safety Monitoring Board (DSMB). The DSMB will determine if there is sufficient evidence of efficacy benefit to justify continuation of the trial to its completion. This futility assessment will be based on the conditional power of the trial derived under various relative risk reduction assumptions. Following this assessment, the DSMB may recommend terminating the trial.

Full details will be described in the DSMB charter and Statistical Analysis Plan.

#### 8.2.4 Exploratory Analyses

##### 8.2.4.1 Effect of Prognostic Factors

In order to characterize any potential treatment effect more precisely, an analysis of the primary endpoint will be conducted with the hazard ratio assumed to depend on, in addition to treatment, the following potentially prognostic factors:

- Baseline HDL-C
- Baseline LDL-C
- Baseline TG
- Baseline TC
- Gender
- Age

A factor will be identified as prognostic if the corresponding model term is associated with a p-value of less than 0.2 in a multivariate stratified Cox proportional hazards model that includes all factors. Factors that are determined to be prognostic by this criterion will be included in the final model to provide an estimate of treatment effect that adjusts for factors that are likely to influence the primary endpoint. This will be done on the ITT population.

##### 8.2.4.2 Effect of Lipid Changes and Changes in hsCRP while on Treatment

In order to evaluate risk reduction as it relates to changes or actual values in lipids and hsCRP while subjects are on randomized treatment, additional exploratory analyses will be

conducted on the primary endpoint. These will include, but will not necessarily be limited to, analyses that:

- include changes or actual values in lipids and hsCRP as time-dependent covariates in proportional hazard regression models
- take a subset of subjects who are event free at 6 months and use the change from baseline in lipids and hsCRP (or actual values) at that time as fixed covariates in a regression analysis of subsequent events.

In all analyses, randomized treatment will be both included and excluded as a factor in the regression models in order to evaluate if there are additional effects of treatment beyond those that are attributable to changes in lipid levels. These analyses would be conducted on the ITT population.

#### 8.2.4.3 Sensitivity Analyses

If a statistically significant treatment effect is demonstrated in the analysis of the primary endpoint, the robustness of the results will be evaluated with respect to their potential dependence on the assumptions made.

In particular, the effect of censoring subjects who are lost to follow-up (while event free) will be evaluated by imputing event outcomes for such subjects in the analysis. Various imputation rules will be applied and will be established prior to database closure and the breaking of the blind. The sensitivity of the primary analysis to treatments or procedures that would be expected to affect the primary endpoint will be assessed by additionally censoring such subjects at the time of the treatment or procedure.

The consistency of treatment effect across the ACS index event strata and across regions will be tested using a term of treatment by strata interactions in the Cox regression model. Interaction will be considered significant if  $p < 0.1$  and in the event that significant interactions are observed, estimates of treatment effect will only be reported by strata.

#### 8.2.5 Safety Analyses

All safety parameters will be summarized and presented in tables based on the safety population.

For the evaluations of adverse events and general laboratory data described below, neither tests of hypotheses nor estimates of treatment effects will be reported. It is however anticipated that in some instances there will be numerical treatment differences in the

reported summary statistics that are either of interest or concern; in these instances, more extensive exploratory statistical analyses may be performed. The scope of the analyses cannot be determined a priori; but would be expected to include standard regression methods for estimating relative risks such as odds and hazard ratios.

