### 2.2 Secondary Objectives

Key Secondary objectives of this trial are as listed below:

Time to first occurrence of:

- The composite of cardiovascular (CV) death, resuscitated cardiac arrest, non-fatal MI, non-fatal stroke, or hospitalization for ACS (with electrocardiogram [ECG] abnormalities) requiring coronary revascularization
- The composite of CV death, resuscitated cardiac arrest, non-fatal MI, non-fatal stroke, hospitalization for ACS (with ECG abnormalities), or unanticipated coronary revascularization
- The composite of all cause death, resuscitated cardiac arrest, non-fatal MI, or non-fatal stroke

Other Secondary objectives of this trial are as listed below:

- Assessment of the long-term safety profile of dalcetrapib in this population
- Evaluation of the effects of dalcetrapib on lipids and high-sensitivity C-reactive protein (hsCRP) in this population
- Evaluation of the effects of dalcetrapib on :
  - The composite of CV death, resuscitated cardiac arrest, non-fatal MI, non-fatal stroke, or hospitalization for new or worsening heart failure
  - The composite of CV death, resuscitated cardiac arrest, non-fatal MI, non-fatal stroke, hospitalization for ACS (with ECG abnormalities) requiring coronary revascularization, or hospitalization for new or worsening heart failure
  - The composite of all-cause death, resuscitated cardiac arrest, non-fatal MI, non-fatal stroke, or hospitalization for new or worsening heart failure
  - Fatal or non-fatal MI
  - All-cause death

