1. INTRODUCTION

The purpose of this statistical analysis plan (SAP) is to present the statistical methodology that will be used for the final analysis of DalCor protocol number DAL-301. This plan also provides a description of the analyses used to produce the tables, figures, and listings that will be included in the final statistical report. This SAP is based on the protocol Version 5 dated 11FEB2021 and on the annotated case report form (CRF) version 3.1. In case of differences between the SAP and the protocol, the SAP will supersede the protocol. Any deviation to this SAP would be reported in the statistical report.

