2.2 Study Objectives

The primary objective of this trial is to evaluate the potential of dalcetrapib to reduce cardiovascular morbidity and mortality (cardiovascular [CV] death, resuscitated cardiac arrest, non-fatal myocardial infarction [MI] and non-fatal stroke) in subjects with a documented recent ACS and the AA genotype at variant rs1967309 in the ADCY9 gene.

The secondary objective of this trial is to evaluate the potential of dalcetrapib to reduce other clinically important events, such as hospitalization for ACS (with ECG abnormalities) or unanticipated coronary revascularization as well as hospitalization for new or worsening heart failure, in combination with the primary endpoint.

Additional objectives of this trial are as listed below:

- Evaluation of the effects of dalcetrapib on lipids and high-sensitivity C-reactive protein (hsCRP) in this population
- Assessment of the long-term safety profile of dalcetrapib, including on diabetes, in this population

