6.5 Safety Analysis

All safety parameters will be summarized and presented in tables based on the ITT population.

For the evaluations of adverse events and general laboratory data described below, neither tests of hypotheses nor estimates of treatment effects will be reported, unless otherwise specified. It is, however, anticipated that in some instances there will be numerical treatment differences in the reported summary statistics that are either of interest or concern; in these instances, more extensive exploratory statistical analyses may be performed. The scope of the analyses cannot be determined a priori, but would be expected to include standard regression methods for estimating relative risks such as odds and hazard ratios.

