6.5.2 Adverse Events and Serious Adverse Events

In general, treatment groups will be compared with respect to the incidence of AEs and SAEs overall and by body system.

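### No adverse event or serious adverse event category has a planned treatment difference with an interval; estimates are optional and follow only once a difference has been noticed

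*Protocol*

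**What the plan says.** Protocol 8.2.5 sets the default for AEs and general laboratory data: "neither tests of hypotheses nor estimates of treatment effects will be reported". It then expects that some numerical differences in the summaries will attract interest or concern, and says that "in these instances, more extensive exploratory statistical analyses may be performed". On what those analyses would be, it says "The scope of the analyses cannot be determined a priori; but would be expected to include standard regression methods", and names odds and hazard ratios as examples.

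SAP 6.5 keeps the same structure but adds an exception: "neither tests of hypotheses nor estimates of treatment effects will be reported, unless otherwise specified". The SAP governs, since "In case of differences between the SAP and the protocol, the SAP will supersede the protocol".

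SAP 6.5.2 states that in general "treatment groups will be compared with respect to the incidence of AEs and SAEs overall and by body system". What follows in 6.5.2.1 to 6.5.2.3 is counts and simple per-arm proportions for treatment-emergent AEs, SAEs, AEs leading to drug withdrawal and AEs leading to study withdrawal. SAP 6.5.2.4 lists deaths. No contrast between arms is defined in any of these sections.

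Long-term safety is an objective in both documents: "Assessment of the long-term safety profile of dalcetrapib in this population" (Protocol 2.2) and "Assessment of the long-term safety profile of dalcetrapib, including on diabetes, in this population" (SAP 2.2).

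**The concern.** The plan announces a comparison of AE and SAE incidence but defines no measure for it, and its default bars the natural one. Wanting to avoid hundreds of p-values is a good reason to bar tests. It is not a reason to bar intervals. Without a planned interval, the report can say that no notable difference was seen. It will not say how large an excess the data exclude, which is what a trial of this size can contribute on safety.

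The second part concerns the estimates that do appear. The only route to an AE or SAE effect estimate runs through someone first noticing a difference. There is no threshold, event list or scope fixed in advance. If the size of the observed difference influences what is picked, the reported estimates lie further from no effect than the truth does, on average, and their nominal intervals can cover too rarely.

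**Working it through.** **Does the SAP's exception clause reach AEs?** Reading SAP 6.5.1 to 6.5.6 for analyses that go beyond description gives two. HbA1c change to 6 months is analysed by the ANCOVA of SAP 6.4.3, which is reported with 95% CI and p-value. New-onset diabetes gets a stratified Cochran-Mantel-Haenszel test (6.5.5), with no estimate or interval named. Nothing in 6.5.2.1 to 6.5.2.4 makes an exception, so for AE and SAE incidence the bar stands.

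**What bounds would planned intervals give?** The documents give no AE rates and no figure of their own on this point, so incidences are assumed. SAP 6.1 gives 6149 randomized, and allocation is 1:1, so n = 6149/2 = 3074.5 per arm. With equal incidence p in both arms, the 95% half-width of the risk difference is 1.96 × √(2p(1−p)/n):

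- p = 25%: 1.96 × √(0.375/3074.5) = 2.16 points
- p = 5%: 1.96 × √(0.095/3074.5) = 1.09 points
- p = 1%: 1.96 × √(0.0198/3074.5) = 0.50 points

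If the analysed number is lower than the number randomized, these widen with 1/√n. For example, 1% fewer subjects widens them by a factor of 1/√0.99 = 1.005.

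**How much could selection inflate an estimate?** The plan states no selection rule, so the cut-offs below are assumptions that show a range. For each scenario, 400,000 trials were simulated with 3074 per arm and a true risk ratio (RR) of 1.20. The table gives the geometric mean of the estimated RR among trials in which the estimate would be shown.

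| Placebo incidence | No selection | Shown if z>1 | z>1.645 | z>1.96 |
|---|---|---|---|---|
| 0.5% | 1.21 | 1.81 | 2.18 | 2.44 |
| 1% | 1.20 | 1.53 | 1.73 | 1.85 |
| 2% | 1.20 | 1.37 | 1.48 | 1.54 |
| 5% | 1.20 | 1.25 | 1.30 | 1.33 |

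The 5% row can be checked by hand.

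- SE(log RR) = √(0.95/153.7 + 0.94/184.4) = 0.106, so the mean z is ln(1.20)/0.106 = 1.72.
- For z>1, the mean of the truncated normal is 1.72 + φ(−0.72)/Φ(0.72) = 1.72 + 0.309/0.763 = 2.12, and exp(2.12 × 0.106) = 1.25.
- For z>1.96, it is 1.72 + 0.387/0.404 = 2.68, and exp(2.68 × 0.106) = 1.33.

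With selection in either direction at |z|>1.645, coverage of a nominal 95% CI falls to 83% at 1% incidence. At 5% incidence it stays at 95%. The problem is therefore mainly one of rarer events.

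**The case against.** Descriptive AE tables with follow-up of signals are a coherent and openly stated choice, and several facts limit the harm.

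- *Parts of safety are estimated elsewhere.* HbA1c and new-onset diabetes, the aspect that the SAP's safety objective names, have planned analyses. Under Protocol 7.1.1.4, positively adjudicated endpoint events are exempt from SAE reporting. The cardiovascular events enter the Cox models of SAP 6.4.1 and 6.4.2, which include a heart-failure composite. This stands, although HbA1c is measured only to 6 months and the diabetes test names no interval.
- *The bounds can be computed.* Counts and proportions by arm are tabulated, so a crude risk difference and CI follow by arithmetic. This stands too. It also shows how little the fix costs, and leaving the calculation to readers does not make it part of the plan.
- *The candidates are visible and the follow-up is called exploratory.* The organ-class and preferred-term tables show every term that could have been chosen. What is missing is a statement that a given estimate was chosen after the tables were seen.
- *Size is not the stated trigger.* The wording leaves room for clinical judgement and makes the analyses optional. The z cut-offs are therefore illustrations, not the plan's rule.
- *A crude risk difference has no fixed time horizon*, because Protocol 3.1 sets no minimum or maximum treatment duration. That is so, but it applies equally to the simple proportions the SAP already reports, and the difference is taken between arms randomized 1:1.

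A reader might go further and infer that the safety objective gets no bounds at all, that an excess cannot be ruled out from the reported tables, or that every AE estimate that appears will be inflated. The documents support none of these. The first is contradicted by the HbA1c analysis, the second by the tabulated counts, and the third by the optional, judgement-based trigger.

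**Conclusion.** The point holds for AE and SAE incidence. The default is no estimate, the only route to one depends on the data, and the comparison promised in SAP 6.5.2 has no planned measure or interval. It does not extend to HbA1c, new-onset diabetes or adjudicated cardiovascular events.

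Inflation of selected estimates is an expected tendency, not a certainty for any one estimate. Under the assumed cut-offs and a true RR of 1.20, it is modest at 5% incidence (1.25 to 1.33) and substantial at 1% (1.53 to 1.85). These figures rest on assumed event rates, an assumed true effect and assumed selection rules, because the documents give none.

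No primary or confirmatory conclusion is affected. This is an inexpensive improvement to safety reporting.

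**What to change.** In SAP 6.5, keep the bar on hypothesis tests for AEs and replace the bar on estimates with a short fixed rule along these lines:

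*For any treatment-emergent AE, any SAE, AEs leading to premature drug withdrawal and AEs leading to premature study withdrawal, the difference in the proportion of subjects (dalcetrapib minus placebo) will be presented with a 95% CI and no p-value. These intervals are descriptive and not adjusted for multiplicity. Any other AE effect estimate chosen after review of the tables will be labelled post hoc.*

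Intervals by organ class are optional. They add information but also more chance findings.

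The cost is SAP wording and a few table rows, with no change to data collection, trial conduct or alpha. The downside is that an unadjusted interval may exclude zero by chance. If the four intervals were independent and there were no true effect, the probability of at least one doing so would be 1 − 0.95⁴ = 19%. The categories overlap, so this is only a rough guide. A footnote saying that the intervals are unadjusted covers it.
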